# Hyperkalaemia monitoring over time

• Absolute value, change and percentage change from baseline in serum K+ level (central labs) by visit and treatment.

#### **Hypotension**

Symptomatic hypotension/decreased blood pressure will be evaluated by the analysis of BP measurements and the analysis of pre-defined AE preferred terms related to hypotension, as well as discontinuations due to hypotension. Hypotension will be presented as Number (%) of patients with:

- SBP<90 mmHg
- DBP <60 mmHg
- SBP<90 mmHg or DBP <60 mmHg\*
- SBP<90 mmHg and DBP <60 mmHg\*

- SBP<90 mmHg and decrease from baseline of >10mmHg\*
- DBP<60 mmHg and decrease from baseline of >10mmHg\*

All the BP outliers will be presented based on the on-treatment definition.

\* Recorded within the same measurement (or at a maximum within the same hour).

An overall summary table of frequencies of AE, SAEs, DAEs, and a summary table by PT will be provided based on a pre-defined list of preferred terms included in the Appendix C: List of preferred terms. The summary will be provided for all the AE with an onset date, or worsening, on or after first dose of investigational medical product (IMP) and within 28 days after last dose of IMP and for the on-treatment definition included in section 4.11.2 overall and by eGFR categories.

The number and percentage of cases will be tabulated by each treatment group.

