9.4.5.6 Safety Topics of Interest

Hyperkalaemia

Hyperkalaemia will be evaluated by the analysis of serum/plasma K⁺ levels (eg, absolute values and change from baseline, values outside predefined ranges, values meeting protocol-defined discontinuation criteria for hyperkalaemia). Further details will be provided in the SAP.

Hypotension

Symptomatic hypotension/decreased blood pressure will be evaluated by the analysis of BP measurements (eg, values outside predefined ranges) and the analysis of pre-defined AE PTs related to hypotension, as well as discontinuations due to hypotension. Further details will be provided in the SAP.

Deteriorating Renal Function

Deteriorating renal function will be evaluated by analysis of serum creatinine and eGFR values (eg, percent change from baseline in eGFR, absolute values and change from baseline, values meeting protocol-defined discontinuation criteria for deteriorating renal function) and analysis of pre-defined AE PTs related to deteriorating renal function. Further details will be provided in the SAP.

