### **4.11 Safety Evaluation**

All safety summaries and analyses will be based upon the SS.

Safety summaries will be presented by treatment group and by eGFR categories ( $<30 \text{ mL/min}/1.73 \text{ m}^2$ ; or  $\ge 30 \text{ to} < 45 \text{ mL/min}/1.73 \text{ m}^2$ ), where appropriate. Individual safety and tolerability data will be provided in data listings.

Where applicable, data will be summarised for the observed value, and for the corresponding change from baseline. Change from baseline will be calculated as the differences between the post-dose value at each time point and the value prior to administration of the study medication.

TP-GDO-WW-016-08 Effective Date: 26 Nov 19 Related to: SOP-GDO-WW-019 CONFIDENTIAL Project Document Version No. 3.0

**Project Document Effective Date**: Date of last signature
Page 25 of 50

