#### Hyperkalaemia

Hyperkalaemia will be evaluated by the analysis of serum/plasma  $K^+$  levels (absolute values, change and percentage change from baseline in  $K^+$ , values meeting protocol-mandated discontinuation criteria for hyperkalaemia) and analysis of pre-defined AE preferred terms related to hyperkalaemia.

Hyperkalaemia will be presented as:

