# Appendix C: List of preferred terms defining the safety topics of interest

The PTs are based on MedDRA version 23.1 and these will be updated with the current MedDRA version for consistency.

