# **Hypotension**

- Hypotension
- Diastolic hypotension
- Orthostatic hypotension

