# **Deteriorating renal function**

- Acute kidney injury
- Acute phosphate nephropathy
- Anuria
- Azotaemia
- Continuous haemodiafiltration
- Dialysis
- Foetal renal impairment
- Haemodialysis
- Haemofiltration
- Neonatal anuria
- Nephropathy toxic
- Oliguria
- Peritoneal dialysis
- Prerenal failure
- Renal failure
- Renal failure neonatal
- Renal impairment
- Renal impairment neonatal
- Subacute kidney injury

TP-GDO-WW-016-08 CONFIDENTIAL Effective Date: 26 Nov 19 Project Document Effective Date: Date of last signature Related to: SOP-GDO-WW-019

Page 50 of 50

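### The SAP's general by-eGFR safety breakdown omits the eGFR ≥ 45 group, and Appendix C does not match the hypotension and hyperkalaemia topics it serves

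*SAP*

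**What the plan says.** **eGFR groups.** SAP 4.11 states: "Safety summaries will be presented by treatment group and by eGFR categories". The parenthesis that follows names two groups, < 30 and ≥ 30 to < 45 mL/min/1.73 m², and the sentence applies where appropriate. SAP 4.11.3 opens by naming three groups, the third being ≥ 45. SAP 4.11.2 asks for adverse-event tables for every eGFR category, without restating the cut-points.

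**Hypotension.** SAP 4.11.3 introduces the topic with: "Symptomatic hypotension/decreased blood pressure will be evaluated by the analysis of BP measurements and the analysis of pre-defined AE preferred terms related to hypotension". Protocol 9.4.5.6 gives it the same scope. The SAP then asks for a summary of adverse events, serious adverse events and adverse events leading to discontinuation, plus a table by preferred term, both from the list in Appendix C. That list has three entries: Hypotension, "Diastolic hypotension" and "Orthostatic hypotension".

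**Hyperkalaemia.** SAP 4.11.3 includes an "analysis of pre-defined AE preferred terms related to hyperkalaemia". Appendix C is titled "List of preferred terms defining the safety topics of interest", but has headings only for hypotension and for deteriorating renal function. The renal list ends with "Subacute kidney injury" on the last page of the SAP. In Protocol 9.4.5.6 the topic rests on laboratory values alone: "Hyperkalaemia will be evaluated by the analysis of serum/plasma K⁺ levels".

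**The concern.** Hyperkalaemia, hypotension and deteriorating renal function are the risks on which the plan concentrates its safety assessment, and Protocol Table 2 calls hyperkalaemia the primary concern with this mechanism. The tables for these topics, and the safety summaries by renal function, should be producible from the SAP without further decisions.

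Two of the three gaps are rules that give a poorer result if a programmer follows them. A two-group list removes the patients with the best renal function from the general by-eGFR summaries, so the reference end of the comparison is missing there. A closed list of hypotension-worded terms leaves out events that the topic's own title covers. The third gap is a promised analysis with no definition. If its terms are chosen after the data are known, they are no longer pre-defined.

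**Working it through.** The plan gives no figure for this point, so there is nothing to reproduce. The check sets the sections side by side, with one line of arithmetic.

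**1. eGFR groups across the SAP**

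| SAP section | Use | Groups (mL/min/1.73 m²) |
|---|---|---|
| 4.6.1 | Stratification summary | 20 to < 30; 30 to < 45; ≥ 45 |
| 4.7 | Baseline disease characteristics | < 30; 30 to < 45; ≥ 45 |
| 4.10.1.7 | Efficacy subgroups | < 30; 30 to < 45; ≥ 45 |
| 4.11 | General safety summaries | < 30; 30 to < 45 |
| 4.11.2 | Adverse-event tables | each category, cut-points not restated |
| 4.11.3 | Safety topics | < 30; 30 to < 45; ≥ 45 |

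Section 4.11 is the only one that stops at two. Sections 4.11.1 and 4.11.4 to 4.11.6 (exposure, laboratory, ECG, vital signs) set no eGFR groups of their own, so any eGFR split of those outputs would take its groups from 4.11. Section 4.11.2 requires every category, which conflicts with 4.11 unless the third group is restored.

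**2. Size of the unlisted group**

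Inputs: a cap of 35% on eGFR ≥ 45 (Protocol 4.1; SAP 3.1) and about 500 randomised, 125 per arm (Protocol 9.2; SAP 4.13).

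- Overall: 0.35 × 500 = 175 at most.
- Per arm, if spread evenly: 0.35 × 125 = 43.75, about 44 at most.

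These are ceilings on the size of the group. They are not counts of patients lost from the safety analysis.

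**3. Hypotension list against its topic**

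- The topic covers both hypotension and decreased blood pressure.
- Appendix C lists three terms. None is worded as decreased blood pressure.
- Protocol 8.3.5 allows a deterioration in a protocol-mandated vital sign to be reported as an adverse event only if it is serious, causes treatment to stop, or is judged clinically relevant. A decreased-blood-pressure event that reaches the database has already passed one of those conditions.
- If it is coded outside the three terms, it does not enter the topic's adverse-event tables. It still appears in the tables by system organ class and preferred term, and in the listing (SAP 4.11.2).
- The documents give no event rates or coding shares, so the number of such events cannot be calculated.

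**4. Hyperkalaemia list against its topic**

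- Appendix C holds 0 hyperkalaemia terms, 3 hypotension terms and 19 renal terms. The only update it foresees is to the MedDRA version.
- The itemised hyperkalaemia outputs in SAP 4.11.3 are confirmed potassium above 5.5 and above 6 mmol/L, same-day local and central pairs, discontinuation criteria met, discontinuations, and change over time. None of them uses Appendix C.
- The preferred-term analysis promised in the same section therefore cannot be produced as specified, while the laboratory analyses can.

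**The case against.** The strongest reply is that these are drafting slips that hide nothing. The two-group list in 4.11 is qualified and reads like an omitted phrase. The SAP asks for terms related to hypotension, and Appendix C supplies three. Low readings are counted directly, in six systolic and diastolic categories that do not use the list. Protocol 8.3.5 asks sites to prefer the clinical to the laboratory term, which should steer reports towards hypotension. Every coded event appears in the general tables whatever its term. For hyperkalaemia, the protocol asks only for potassium values.

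Most of this stands, and it limits the point. A reader might infer more than the documents support:

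- *That hyperkalaemia is undercounted.* With no list, the term-based count has no value at all, and the potassium counts are unaffected.
- *That patients with eGFR ≥ 45 are dropped from the safety analysis, or that up to 175 are lost.* They remain in the Safety Set, in every by-treatment table and in the three-group topic analyses.
- *That the renal gradient in the three named risks cannot be read.* SAP 4.11.3 presents those risks in all three groups.
- *That the safety committee would be misled.* Neither Protocol 9.6 nor SAP 4.11.8 ties its review to Appendix C or to the list in 4.11.

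The reply does not remove the gaps themselves. The preference for clinical terms applies only where possible. Supine readings at scheduled site visits (Protocol 8.2.2) do not replace adverse events that occur between visits. An apparent slip in the governing safety section still conflicts with other sections.

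**Conclusion.** The point holds as a set of three inconsistencies in the SAP, each correctable in a line or a short list.

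The general by-eGFR safety breakdown, as written, omits one of three groups, which may hold at most 35% of patients. The ceiling of 175 assumes the planned 500 and a cap that is fully used.

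The hypotension term list is narrower than the topic it defines. The topic table for adverse events, serious adverse events and discontinuations can miss decreased-blood-pressure events that the general tables still show. This assumes that some such events are coded to terms outside the three listed. Their number is unknown and may be small.

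The hyperkalaemia preferred-term count is undefined. By itself that would be missing detail, and it can be resolved in either direction because the protocol does not require the analysis.

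The primary efficacy analysis and the laboratory and blood-pressure threshold counts are not affected.

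**What to change.** Issue a new SAP version before database lock, as the SAP Introduction provides for changes at that stage. SAP 4.10.1.6 has the interim outputs follow the SAP's methods, so before those are produced is better.

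1. In 4.11, add ≥ 45 mL/min/1.73 m² so that the groups match 4.11.3.
2. In Appendix C, add to the hypotension list the preferred terms for decreased blood pressure in the MedDRA version in use.
3. Reconcile the hyperkalaemia paragraph of 4.11.3 with Appendix C: either add a hyperkalaemia term list, or delete the preferred-term analysis and rely on the potassium outputs already itemised.

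The cost is SAP wording and minor programming. No data collection, sample size or protocol text changes. The one visible consequence is that hypotension topic counts may rise slightly.

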# **Deteriorating renal function**

Deteriorating renal function will be evaluated by analysis of serum creatinine and eGFR values (percent change from baseline in eGFR, absolute values and change from baseline, values meeting protocol-defined discontinuation criteria for deteriorating renal function) and analysis of pre-defined AE preferred terms related to deteriorating renal function.

Deteriorating renal function will be presented as:

### Deteriorating renal function related safety topics of interest

- Number (%) of patients with a decrease in eGFR of  $\geq 25\%$ ,  $\geq 30\%$ ,  $\geq 40\%$  and  $\geq 57\%$ from baseline at any visit during the randomized treatment period (based on central lab values). These decreases would need to be confirmed by another central eGFR measure. Summary will be based on the on-treatment definition included in section 4.11.2
- Number (%) of patients who met the protocol mandated renal discontinuation criteria in the study:
  - At any visit during the randomized treatment period eGFR >50% decline from baseline and/or decrease to an absolute value <15 ml/min/1.73 m^2 confirmed with eGFR >50% decline from baseline and/or decrease to an absolute value <15 ml/min/1.73 m^2 (based on central lab values).

Confirmation has to be the next consecutive central lab sample which is  $\leq 14$  days of the original central lab sample.

Additional analysis will include eGFR lab values confirmed at the next consecutive central lab sample regardless of time from initial lab sample.

- Number (%) of patients with >25% residual decrease in eGFR at safety follow-up visit compared to baseline
- Number (%) of patients who discontinued due to meeting the protocol mandated renal discontinuation criteria in the study

†Based on the end of treatment CRF page

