7.1 Discontinuation of Study Intervention

It may be necessary for a participant to permanently discontinue (definitive discontinuation) study intervention.

Participants may be discontinued from study intervention in the following situations:

- Participant decision. The participant is at any time free to discontinue treatment, without prejudice to further treatment
- An AE that, in the opinion of the Investigator or AstraZeneca, warrants discontinuation from further dosing
- Severe non-compliance with the CSP
- Safety reasons as judged by the investigator and/or sponsor where continued treatment may put participant at undue risk

Participants will be discontinued from study intervention in the following situations:

- If the participant becomes pregnant during the course of the study
- Protocol-defined hyperkalaemia: Study treatments must be discontinued in case of confirmed (ie, 2 consecutive samples) serum/plasma K⁺ > 6.0 mmol/L, or confirmed serum/plasma K⁺ > 5.5 mmol/L (at investigator's discretion), or serum/plasma K⁺ > 5.5 mmol/L with repeat value > 6 mmol/L (see Appendix F 1 for details on the monitoring and management of hyperkalaemia)
- Protocol-defined deteriorating renal function: Study treatments must be discontinued in case of confirmed eGFR reduction from baseline > 50% and/or any confirmed decrease below 15 mL/min/1.73 m² (see Appendix F 2 for details on the monitoring and management of deteriorating renal function)
- There have been reports of ketoacidosis, including DKA, in patients with T2DM taking dapagliflozin and other SGLT2 inhibitors in previous studies. Patients with T2DM on investigational treatment who present with signs and symptoms consistent with ketoacidosis, including nausea, vomiting, abdominal pain, malaise and shortness of breath should be assessed for ketoacidosis, even if blood glucose levels are < 14 mmol/L (250 mg/dL). If ketoacidosis is suspected, discontinuation or temporary interruption of the investigational treatment should be considered and the patient should be promptly evaluated.

Note that discontinuation from study intervention is NOT the same thing as a withdrawal from

the study.

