BSA=body surface area; CKD-EPI=chronic kidney disease epidemiology collaboration; eGFR=estimated glomerular filtration rate; HbA1c=glycated haemoglobin; HDL-C= high density lipoprotein cholesterol; K⁺=potassium; LDL-C=low density lipoprotein cholesterol; MCHC=mean corpuscular haemoglobin concentration; MCV=mean corpuscular volume; Na⁺=sodium; RT-PCR=reverse transcriptase polymerase chain reaction; SARS-CoV-2=severe acute respiratory syndrome coronavirus 2; SoA=schedule of activities; ULN=upper limit of normal; VLDL-C= very low density lipoprotein cholesterol

- ^a Local laboratory at screening and pre-randomisation (if applicable per SoA) and central laboratory at subsequent visits, unless specified otherwise.
- ^b At the local laboratories, electrolytes (Na⁺ and K⁺) and creatinine may be measured in plasma samples instead of serum samples depending on their capability.
- ^c Central laboratory measurements for K⁺ levels will be with serum and plasma samples.
- ^d eGFR (mL/min/1.73 m²) will be calculated using the BSA-adjusted CKD-EPI formula and including both serum creatinine and serum cystatin C for central laboratory assessments; and with serum/plasma creatinine alone for local laboratory assessments.
- ^c The post-randomisation INR measurements may be done at a local laboratory if the necessary material provided by the central laboratory is not available; and the measurements may be omitted if the local laboratory is not capable of doing the measurements. Refer to Laboratory Manual for details.
- ^f These tests are not required at screening or pre-randomisation.
- ^g Per Friedewald equation.
- ^h Central laboratory for all cystatin C measurements.

Instructions for the collection and handling of the samples will be provided in the study specific Laboratory Manual.

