contributed to hyperkalaemia; and/or continuation with reassessment; or permanent discontinuation.

- If the repeat local laboratory sample has serum/plasma $K^+ \le 5.5 \text{ mmol/L}$, then study treatments can be resumed, even if the central laboratory sample has serum $K^+ > 6.0 \text{ mmol/L}$.

If the investigator is aware of any change in the participant's clinical status that may influence serum electrolyte levels or fluid balance (eg, vomiting and/or diarrhoea > 1 day), it is recommended to reassess serum/plasma K^+ levels as soon as possible after the acute event. In case of permanent discontinuation, serum/plasma K^+ levels should be monitored until resolution or stabilisation.

F 2 Deterioration of Renal Function

Serum creatinine will be measured both at a local laboratory and a central laboratory at all baseline and on-treatment visits according to the SoA. Repeat samples should be sent for both central and local laboratory assessment. It is expected that local laboratory results will be available prior to central laboratory results. As local and central laboratories will calculate eGFR using different formulas, central eGFR values should always be compared to central eGFR values and local eGFR values should always be compared to local eGFR values. For local laboratories, the eGFR assessment at Visit 3 (prior to the start of study treatment) will be taken as the baseline eGFR value.

- If eGFR shows a 30-50% decline from baseline and an absolute value ≥ 15 mL/min/1.73 m² (based on local and/or central laboratory samples), eGFR should be reassessed within 1 week.
 - If persistent 30-50% decline stabilises upon weekly follow-ups, eGFR monitoring may return to the standard SoA, at investigator's discretion.
- If eGFR shows a >50% decline from baseline and/or decreases to an absolute value < 15 ml/min/1.73 m² (based on local and/or central laboratory samples), eGFR should be reassessed within 48 hours.
 - If eGFR shows a 30% to 50% decline from baseline and an absolute value $\geq 15 \text{ mL/min/1.73 m}^2$, eGFR should be reassessed within 1 week.
 - If eGFR again shows a >50% reduction from baseline and/or absolute value
 <15 mL/min/1.73 m², study treatments must be discontinued immediately and eGFR should be followed up within a week and weekly until signs of improvement and stabilisation.

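### The SAP row for patients meeting the protocol's renal stopping rule uses central eGFR only, while the protocol applies the rule to local and/or central eGFR

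*SAP*

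**What the plan says.** **Protocol.** Section 7.1 requires study treatment to stop for "confirmed eGFR reduction from baseline > 50% and/or any confirmed decrease below 15 mL/min/1.73 m²". It names no laboratory and refers to Appendix F 2 for detail. There, the trigger for a fall of more than 50% and/or a value below 15 is "based on local and/or central laboratory samples), eGFR should be reassessed within 48 hours", and repeat samples go to both laboratories. A second breach requires immediate discontinuation, and that confirming step names no laboratory. On baselines, "central eGFR values should always be compared to central eGFR values and local eGFR values should always be compared to local eGFR values", and "For local laboratories, the eGFR assessment at Visit 3 (prior to the start of study treatment) will be taken as the baseline eGFR value". On timing, "It is expected that local laboratory results will be available prior to central laboratory results".

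The laboratories use different equations. Under Table 6 in Section 8.2.4, central eGFR uses creatinine and cystatin C, "and with serum/plasma creatinine alone for local laboratory assessments". Section 9.4.5.6 lists among the planned renal analyses "values meeting protocol-defined discontinuation criteria for deteriorating renal function" and leaves further detail to the SAP.

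**SAP.** Section 4.11.3 labels one row as patients who met the protocol-mandated renal criteria. It defines a breach as a fall of more than 50% and/or "absolute value <15 ml/min/1.73 m 2 (based on central lab values"), confirmed by the next central sample within 14 days. An additional analysis drops the time limit but remains central only. A separate row counts patients who discontinued for meeting the criteria, apparently from the end-of-treatment CRF page. Section 4.14 declares no change to the planned analysis.

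**The concern.** The row carries the protocol rule's name but implements a narrower rule. A patient whose local creatinine-based eGFR breaches twice, while central eGFR does not, has met the protocol rule and is absent from the row.

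Deteriorating renal function is one of three designated safety topics, so this count will be read as the number who reached the protocol's renal limit. Two things can go wrong:

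- A patient stopped on local values can appear as discontinued for meeting the criteria while the adjacent row says the criteria were not met.
- A patient who met the rule locally but was not stopped appears in neither row, although such a departure is what a met-criteria row should expose.

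**Working it through.** The plan gives no figure to reproduce. The check compares the texts, then asks whether the two laboratories can disagree at the thresholds.

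**1. The two rules**

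| Element | Protocol 7.1 and Appendix F 2 | SAP 4.11.3 row |
|---|---|---|
| Trigger | Local and/or central | Central |
| Confirmation | Laboratory not named; repeats go to both | Next central sample |
| Baseline | Own laboratory's (local: Visit 3) | Central |

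No reading of the protocol yields a central-only rule.

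**2. Inputs.** From Protocol 8.2.4 and SAP Appendix B: the local creatinine exponent is -1.209, the central creatinine exponent -0.601, and the central cystatin C exponent above 0.8 mg/L has size 0.711. The text as read shows no minus sign on 0.711. I take it as negative, because the companion term below 0.8 mg/L has exponent -0.375 and eGFR should not start to rise with cystatin C above that point. Results at k = 0 do not depend on this.

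Let R be the fold-rise in creatinine (above kappa) and k the log-rise in cystatin C divided by the log-rise in creatinine. The value of k is an assumption, so a range is shown.

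- Local eGFR is multiplied by R^(-1.209).
- Central eGFR is multiplied by R^(-(0.601 + 0.711k)).

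**3. The >50% limb.** Local eGFR halves at R = 2^(1/1.209) = 1.774. The central fall at that point is:

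| k | 0 | 0.25 | 0.5 | 0.75 | 1 |
|---|---|---|---|---|---|
| Central fall | 29% | 36% | 42% | 48% | 53% |

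The SAP row misses the patient when k < (ln 2/ln R - 0.601)/0.711:

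- R = 1.774: k < 0.855 (cystatin C up less than 1.63-fold)
- R = 2.0: k < 0.561 (1.475-fold)
- R = 2.5: k < 0.219 (1.222-fold)
- R above 2^(1/0.601) = 3.169: no miss unless cystatin C falls

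With equal rises (k = 1), central eGFR halves first, at R = 2^(1/1.312) = 1.696, and nothing is missed.

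Example: a man aged 72, not in the equations' Black category, with creatinine rising from 2.0 to 4.0 mg/dL and cystatin C steady at 2.0 mg/L. Local eGFR goes from 32.4 to 14.0 (down 56.7%), breaching both limbs. Central eGFR goes from 30.4 to 20.0 (down 34.1%), breaching neither. If cystatin C also rose to 3.0 mg/L, central eGFR would be 15.0, down 50.6%, and the central rule would be met.

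**4. The <15 limb.** Assume the same baseline B in both laboratories. Local eGFR reaches 15 at R = (B/15)^(1/1.209).

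| B | R | Central, k = 0 | Central, k = 0.5 | Central, k = 1 |
|---|---|---|---|---|
| 20 | 1.269 | 17.3 (-13%) | 15.9 (-20%) | 14.6 (-27%) |
| 25 | 1.526 | 19.4 (-22%) | 16.7 (-33%) | 14.4 (-43%) |

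At k = 0 and 0.5 the patient is missed; at k = 1 central also falls below 15.

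**5. Do the SAP's other central rows show the fall?** At the local threshold, the central fall is under 25% when B < 15 × (4/3)^(1.209/(0.601 + 0.711k)). That gives 26.8 at k = 0, 23.4 at 0.25, 21.6 at 0.5 and 20.4 at 0.75. Without any eGFR equation, a central value still at or above 15 means a fall of at most 1 - 15/B: 25% from 20, 40% from 25. On the >50% limb, the smallest missed fall when cystatin C does not decrease is 29%, so the ≥25% row would show it if confirmed centrally.

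**The case against.** The strongest defence is that the choice is printed in the row and the protocol left detail to the SAP. It is consistent with the other renal rows, eGFR over time, the randomisation criterion and stratification, all of which use central values. On this view Section 4.14 is not contradicted, since the protocol's analysis section named no laboratory. The disclosure is real, and it makes the Section 4.14 argument weak. But a delegation of detail does not extend to a narrower criterion under the protocol's name.

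The words local and/or central are attached to the trigger, not the confirming step, and the statement that local results arrive first is only about timing. Both points are correct. The potassium row in the same SAP section accepts local or central confirmation, but it is an imperfect parallel: Appendix F 1 gives local potassium priority for decisions, and Appendix F 2 says nothing similar for eGFR. None of this makes the renal rule central only.

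Much of the information is reported elsewhere. Patients actually stopped should appear in the discontinuation row. Under Protocol 8.3.5 a laboratory deterioration that causes discontinuation is reportable as an adverse event. A patient who met the rule but was not stopped might appear among the important deviations in SAP 4.6.2, though that is not assured. This limits the harm but does not make the row match its label.

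A reader might infer that the whole eGFR 20 to <30 stratum, planned at 20% or more of 500 (about 100 patients), is exposed. The documents do not support that. It is a planned stratum size that depends on the safety committee opening the stratum, and the <15 limb escapes the ≥25% row only at the lowest baselines.

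**Conclusion.** The mismatch holds on the text. A patient who meets the protocol rule on local eGFR alone can be missing from this row and from its any-time version, and the row can contradict the discontinuation count beside it.

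The size in patients is unknown, because no document gives the joint behaviour of creatinine and cystatin C. A miss on the >50% limb requires cystatin C to rise clearly less than creatinine (k below about 0.86 at the local threshold, and lower for larger rises). On the <15 limb, the fall escapes the ≥25% row as well only for baselines of roughly 20 to 27, depending on k. These bounds assume creatinine above kappa, cystatin C above 0.8 mg/L, a negative cystatin C exponent and, for the <15 limb, equal baselines in the two laboratories.

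A reader might also infer that patients go unprotected or that the efficacy result is affected. Neither follows: sites act on Appendix F 2, not on this table, and the primary analysis, alpha and sample size do not use it. It is a labelling and derivation fault in one descriptive row on a designated safety topic, and worth correcting.

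**What to change.** In SAP 4.11.3, count a patient as meeting the criterion when:

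- a local or central eGFR breaches (more than 50% below baseline and/or below 15), with local values judged against the local Visit 3 baseline and central values against the central baseline; and
- the next consecutive repeat, from either laboratory, also breaches against its own laboratory's baseline within the SAP's 14-day window.

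State that the confirming value must come from a later draw, and that either laboratory's result on that draw suffices. Requiring confirmation in the same laboratory would again be narrower than Appendix F 2, which demands same-laboratory comparison with baseline but not same-laboratory confirmation. Extend the any-time analysis in the same way, and keep the central-only count as a separately labelled supportive line. Relabelling alone would remove the false description but leave the protocol's own criterion uncounted.

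The cost is SAP wording and modest derivation code. The Schedule of Activities already has local creatinine with eGFR at Visits 3 to 10, and repeats already go to both laboratories, so no visit or sample is added.
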